
Adjustment of Dose for Musculoskeletal or Other Minor Side Effects. For subjects who develop minor musculoskeletal side effects, such as carpal tunnel syndrome or trigger finger, or other minor side effects such as mild hypoglycemia or hyperglycemia (glucose lower than 65 mg/dL or greater than 100 mg/dL) mild headaches, fluid retention, peripheral swelling, and joint pain in the unoperated leg or other area of the body (these symptoms are likely to be present in the operated limb as a result of surgery) the dose of GH or placebo will be reduced to 0.25mg per BSA BID. For patients

with carpal tunnel or trigger finger, they will also receive treatment consisting of ice (15-20 minutes twice daily) and range of motion exercises, which are the standard care for the onset of carpal tunnel or trigger finger. If the symptoms/abnormal values resolve in 7-10 days, the dose will then be titrated as tolerated at increments of 0.05mg per BSA BID every 7 days until reaching a dose at which symptoms do not appear/abnormal values return to normal, or upon reaching the normal study dose of 0.5mg per BSA BID. If symptoms/abnormal values persist at the dose of 0.25 mg per BSA BID greater than 7-10 days, the dose will be decreased to 0.1 mg per BSA BID and titrated up at increments of 0.05mg per BSA BID every 7 days until reaching a dose at which symptoms do not appear/abnormal values return to normal levels. If symptoms/abnormal values do not resolve after 7-10 days at a dose of 0.1mg per BSA BID, the subjects will be discontinued from the study.

Randomization and Assignment of Groups. Patients will be assigned to placebo or GH treatment groups using a block randomized assignment schedule that maintains equal group sizes. All included patients will be assigned unique identification numbers by [name], clinical research coordinator in [name] lab, with no involvement in this study design or interpretation of any resultant data. [name] will then assign identification numbers in a consecutive fashion to either group "maize" (randomly designated by [name] as either the placebo or treatment group) or group "blue" (the group not selected to be represented as group A). [name] will keep all patient names and assigned identifier lists private in a sealed envelope in a locked cabinet as well as on two separate passcode protected hard drives. He will make the unblinded group identities available to [name], relevant members of the UMHS Pharmacy IDS and safety board members if necessary. Therefore, the patients, investigators, attending physicians, those measuring outcome will be unaware of the allocation of the patients and thus will be blinded.

Risks of Participation. There are some potential risks of GH that will be closely monitored. The risks include: glucose intolerance or reduced insulin sensitivity, fluid retention and peripheral swelling, joint pain, headache, numbness or fatigue, tissue atrophy, pancreatitis, intracranial hypertension, injection site lipoatrophy, and local or systemic allergic reactions. The injection of GH might infrequently cause some slight discomfort and there is a rare risk of infection from injections. There are minimal risks associated with the blood draws -- the needle stick may infrequently hurt and cause bruising, and a rare risk of local infection. There are no known harmful effects from the strong magnetic field used for MRI, although any loose metal object has the risk of causing damage or injury if it gets pulled toward the strong magnet. Strength measurements might infrequently cause some soreness that would last less than a day.

Benefits of Participation. If our hypothesis is supported, patients that receive GH will have improved recovery after ACL-R.

Payment to Subjects. Patients will also receive \$1000 for participating in the study. Patients who drop out prior to completion will receive a pro-rated amount (\$125 per visit).

Outcome Measures. The overall objectives of the study are to evaluate if GH is safely tolerated in closely monitored patients undergoing ACL-R, and if so, to collect pilot and early efficacy data to determine if subsequent larger clinical trials are warranted. The primary outcome measure of the study is isokinetic knee extension strength at 26 weeks. Secondary outcome measures include isokinetic strength at other time points, MRI measurement of muscle size, PROMs, and circulating protein biomarkers (IGF-1, myostatin, MMP-3, and hyaluronic acid).

Sample Size and Statistical Analyses. We base the sample size for this study on maximum isokinetic knee extension values at the time of discharge from our previous study (Mendias 2013). To detect a 30% difference in isokinetic knee strength between the placebo and GH group, with a power of

80% and $\alpha=0.05$, requires $N=17$ per group. To account for any patient attrition, we will aim to recruit 7 additional patients for each group into the study for a total of $N=24$ per group or $N=48$ for the entire study. We will use a mixed-effects linear regression model (Zhang 2010) to look at the changes in individual parameters between the placebo and GH groups at multiple time points over the course of the study, as well as the associations between changes of multiple parameters. We will also perform interim data analysis to determine if there are significant differences in strength and other outcomes between groups.

Data and Safety Monitoring Plan. We will have a committee to oversee the safety and adverse events that may come up in this study. The committee will consist of [name] (endocrinologist), [name] (sports medicine orthopaedic surgeon), and [name] (primary care/sports medicine). All lab reports will be sent to [name] as they occur, and the full committee will review outcomes and patient (surveys, strength measurements, M-Labs blood work reports, injuries, etc.) every 3 months (or as needed) and review. If an excessive number of adverse events or infrequent but serious events happen, the committee will have the ability to halt the study or unenroll patients from the study. The committee may also stop the trial if there are any concerns that GH is causing harm. These potentially serious events that would cause the patient to unenroll from the study include any vital signs rising to levels above those described in the exclusion criteria, or signs of intracranial hypertension, severe fluid retention, severe hyperglycemia. These are potentially serious side effects described from previous clinical trials of GH, and although we cannot predict all potentially serious side effects, we will rely on the clinical expertise of the safety monitoring team to assess any other potentially serious but unexpected risks. In these situations the random code will be broken for that patient and any required care for them will then be initiated. Unblinding for all study team members will occur after the last patient has been discharged from care.

At the conclusion of the study, original data will be archived in the UM Department of Orthopaedic Surgery following FDA guidelines.

Adverse Event Reporting Timetable. We will follow the standard IRB adverse events reporting timeline. Adverse events that are expected and non-serious will be reported to the safety committee at their regular meetings, and to the IRB as part of the scheduled continuation application. Serious adverse events will be reported to the safety committee immediately, and to the IRB within 7 days, and to the FDA as per the regulations.

Regulatory Affairs Coordinator. [name], clinical research manager in the Department of Orthopaedic Surgery, will coordinate safety committee meetings and ensure the study maintains regulatory compliance with federal and state laws, and UM policies.

References

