
Figure 4. Overview of the study time points.

deviate from the standard of care typically provided to patients undergoing ACL-R. An overview of the timeline of study visits is presented in Figure 4 and Table 1. This study is registered on Clinicaltrials.gov (NCT02420353) and was granted an IND exemption by the FDA (IND 123189).

| Study Visit | Measures Performed |
|-------------------------------------|---|
| 1. Preop 1 (~4 wk prior to surgery) | History/vitals, blood draw, vital signs |
| 2. Preop 2 (~2 wk prior to surgery) | Surveys, BioDex (isometric, isokinetic), MRI, medication instruction, vital signs |
| 3. Postop 1 (~1 wk after surgery) | Surveys, blood draw, medication check, vital signs |
| 4. Postop 2 (~2 wk after surgery) | Surveys, blood draw, medication check, vital signs |
| 5. Postop 3 (~5 wk after surgery) | Surveys, BioDex (isometric, isokinetic), MRI, blood draw, medication check, vital signs |
| 6. Postop 4 (~12 wk after surgery) | Surveys, BioDex (isometric, isokinetic, balance), blood draw, vital signs |
| 7. Postop 5 (~18 wk after surgery) | Surveys, BioDex (isometric, isokinetic, balance), blood draw, vital signs |
| 8. Postop 6 (~26 wk after surgery) | Surveys, BioDex (isometric, isokinetic, balance), MRI, blood draw, vital signs, patient discharged from the study |

Table 1. Timeline of study visits and measures performed in this proposal.

Patient Selection and Recruitment. This study is based on an already approved protocol by the University of Michigan Medical School Institutional Review Board (study # HUM00038126). All patients will provide informed consent prior to participating in the study.

Inclusion Criteria:

1. Males between the ages of 18 and 35
2. Have acute unilateral complete ACL tears with or without bucket handle medial meniscus tears that occurred within the past 6 months
3. Consent to undergo an ACL reconstruction by [name] using a patellar tendon or hamstring autograft
4. Will be performing supervised post-operative rehabilitation at UMHS MedSport at Dominos Farms ([name])

Exclusion Criteria:

1. Patients who are undergoing a revision ACL reconstruction
2. Had a previous injury to the involved knee
3. Have an allergy to recombinant GH
4. Have a BMI < 20 or > 35

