After assessing vitals and lab work, patients will be scheduled for an MRI, and for an appointment at MedSport where strength and stability measurements, completion of surveys and instruction on medication use will be performed. All screening and initial study measurements will be performed no more than one week before surgery.

Surgical Reconstruction and Postoperative Rehabilitation. Patients will have a thorough history and physical examination performed by [name]. Examination under anesthesia will be performed to confirm functional instability and document the extent of meniscus tear. Surgical reconstruction of the ACL will be performed using autologous graft from the ipsilateral knee, and a partial meniscectomy or meniscal repair will be performed to repair the meniscal defect. A single-bundle, anatomic “center-center” ACL-R will be performed (Bedi 2009). Patients will follow a standard, supervised accelerated ACL rehabilitation protocol postoperatively (modified from Kim 2003, Beynon 2005a). Rehabilitation begins with quad sets, straight leg raises, ankle pumps, heel slides, and partial weight bearing up to 25% in the first week. These exercises continue into the second and third weeks, with the addition of electrical stimulation for muscle reeducation, leg press, core and hip exercises, stationary biking, and progression to 50% weight bearing. From weeks 4 to 12, additional closed chain resistance exercises are added and patients progress to full weight bearing and open chain exercises. From weeks 12 to 20,

exercises increase in load and complexity, and patients progress to a jogging program. Agility and plyometric training begin at week 20, and continue in complexity and intensity based on passing functional tests demonstrating appropriate gait and motor control.

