Surveys and Recording of Patient-Reported Adverse Events. Patients will complete patient reported outcome measure (PROM) surveys at each visit to measure pain, function and physical performance, including (i) the Veterans Rand-12 (VR-12), to measure overall health-related quality of life (Selim 2009); (ii) the International Knee Documentation Committee (IKDC) survey, to evaluate knee-specific sports function (Anderson 2006), and (iii) the Knee injury and Osteoarthritis Outcome Score (KOOS), to evaluate knee-specific general and sports function (Roos 2003). Patients will also be asked to report adverse events associated with the use of GH, as described in the GH Self Reporting Symptom Form.

BioDex Strength Testing and Ultrasound Muscle Cross-Sectional Area Measurements. Whole muscle isometric and isokinetic strength measurements will be performed in a BioDex System 3 dynamometer as described (Mendias 2013). Maximum isometric force will be measured at 45° and 90° of knee flexion. Maximum isokinetic flexion and extension will be measured over a 90° arc at a velocity of 60°/second. All measures will be performed bilaterally, and the highest force from a series of five trials from each side will be used.

MRI Muscle Volume Measurements. Bilateral MRI scans will be performed at the pre-operative, third post-op and sixth post-op visit. Scans will be performed in a 3.0T magnet and will extend from hip to knee. The volume of the quadriceps and hamstring muscle groups will be determined using quantitative MRI analysis software.

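### Graft type (patellar tendon or hamstring) can affect the measured muscles, but it is neither a randomisation stratum nor a model term; the cost is possible chance imbalance and modest lost precision.

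*Combined protocol and SAP*

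**What the plan says.** Patient Selection and Recruitment (Inclusion Criteria) admits patients who consent to reconstruction "using a patellar tendon or hamstring autograft". It gives no rule for choosing between the two and no expected split. Surgical Reconstruction and Postoperative Rehabilitation fixes the side of harvest: "Surgical reconstruction of the ACL will be performed using autologous graft from the ipsilateral knee".

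The outcomes cover both donor regions in that limb:
- BioDex Strength Testing: "Maximum isokinetic flexion and extension will be measured over a 90° arc at a velocity of 60°/second", and "All measures will be performed bilaterally".
- MRI Muscle Volume Measurements: "The volume of the quadriceps and hamstring muscle groups will be determined using quantitative MRI analysis software".
- Outcome Measures: "The primary outcome measure of the study is isokinetic knee extension strength at 26 weeks".

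Randomization and Assignment of Groups describes a "block randomized assignment schedule that maintains equal group sizes" and names no stratification factor. Sample Size and Statistical Analyses describes a mixed-effects regression "to look at the changes in individual parameters between the placebo and GH groups at multiple time points" and names no covariate.

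**The concern.** Each permitted graft disturbs a muscle-tendon unit whose strength or volume is an outcome in the same limb: the extensor side for a patellar tendon graft, the flexor side for a hamstring graft. Graft type is therefore a plausible source of variation between patients in knee extension, knee flexion and both muscle volumes. In a trial of 17 to 24 patients per arm, the arms can differ in graft mix by chance, and any variation due to graft stays in the residual error.

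Adjusting for baseline strength or volume, which the plan does not mention either, would not solve this. Table 1 places the baseline BioDex and MRI measurements before surgery, so they cannot reflect a harvest that happens later. Graft type needs its own term.

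**Working it through.** **Inputs from the protocol.** Target difference 30%, power 80%, alpha 0.05, 17 per arm, plus 7 per arm for attrition.

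**The plan's own figure.** 17 + 7 = 24 per arm, and 2 × 24 = 48, as stated. The 17 cannot be reproduced independently because no SD is given. Working backwards with a two-sided t-test, 17 per arm at 80% power requires a standardised difference of 0.991. There are two readings of the 30%:
- 30 percentage points: SD = 30 / 0.991 = 30.3.
- 30% relative to the 70% side-to-side ratio implied by the 30% deficit at discharge in the earlier cohort, so 0.30 × 70 = 21 points: SD = 21 / 0.991 = 21.2.

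**Assumed, because the documents are silent.** The graft split p and the graft effect g, in points of strength at 26 weeks. I take p from 50:50 to 90:10 and g from 5 to 20 points.

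**Step 1: chance of imbalance.** With unstratified allocation, treat the number with one graft in each arm as Binomial(n, p). A gap of 20 percentage points or more means a difference of at least 4 patients at n = 17, or 5 at n = 24.

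| Graft mix | n = 17 per arm | n = 24 per arm |
|---|---|---|
| 50:50 | 23% | 19% |
| 80:20 | 13% | 10% |
| 90:10 | 4% | 3% |

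If the overall split is exactly even, the hypergeometric distribution applies and gives 17% and 15%. These are lower because the smallest attainable gap above 20 points is then 5/17 (29 points) or 6/24 (25 points).

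**Step 2: shift in the unadjusted estimate.** Shift = imbalance × g. At a 20-point imbalance this runs from 0.20 × 5 = 1 point to 0.20 × 20 = 4 points. The standard error of the treatment difference at 17 per arm is SD × √(2/17):
- SD 30.3: SE = 10.4 points, so the shift is 1/10.4 = 0.10 to 4/10.4 = 0.38 SE.
- SD 21.2: SE = 7.3 points, so the shift is 0.14 to 0.55 SE.

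**Step 3: precision recovered by adjustment.** The share of variance explained is R² = p(1 − p)g²/SD². The standardised difference becomes 0.991/√(1 − R²). At a 50:50 mix and 17 per arm, ignoring the small loss of degrees of freedom:

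| g (points) | R², SD 30.3 | Power | R², SD 21.2 | Power |
|---|---|---|---|---|
| 5 | 0.7% | 80.3% | 1.4% | 80.5% |
| 10 | 2.7% | 81.1% | 5.6% | 82.2% |
| 15 | 6.1% | 82.4% | 12.5% | 85.0% |
| 20 | 10.9% | 84.3% | 22.3% | 88.8% |

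At an 80:20 mix and SD 30.3, power for g of 10 to 20 points is 80.7% to 82.8%.

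No comparable figures can be given for flexion strength or muscle volume, because the documents supply no target difference or sample-size basis for them.

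**The case against.** The strongest reply is that randomisation already protects the comparison and that the unadjusted standard error already reflects chance differences in covariates. That stands. A reader might infer that the estimate is biased, but the documents do not support this: allocation is random, and the issue is only precision and chance imbalance in one small trial.

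A reader might also infer that imbalance is likely. The figures do not bear that out: even at 50:50, a gap of 20 points is absent in 77% to 81% of trials of this size. The criterion refers to one surgeon, whose mix could be far from even.

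Nothing in the documents gives the size of a graft effect. The Background says that weakness follows reconstruction with any graft type. That does not show that the weakness is equal across grafts or falls on the same muscle group, but it gives no difference either. The 89% power figure needs a 20-point graft effect at SD 21.2, where the treatment target is itself only 21 points, so it is an extreme corner.

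It is tempting to say that graft type is already on record and known before dosing. The protocol says neither. Its criterion requires consent to one graft or the other, not a choice fixed at consent.

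Finally, the model names no covariate at all, not even baseline strength, and the choice between meniscectomy and meniscal repair is also unaddressed. Graft type is thus one gap in a thinly specified model, in a trial described as a pilot. What sets it apart is that harvest directly involves the measured muscle groups, and that no pre-surgical measurement can stand in for it.

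**Conclusion.** The point holds as a low-cost improvement in design and analysis. Two grafts are allowed, both are harvested from the measured limb, and graft type is absent from the allocation scheme and the model. It does not invalidate the primary comparison.

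For the primary outcome the size is modest. The chance of a 20-point imbalance runs from 3% to 23% over the assumed mixes, the resulting shift is mostly a fraction of one standard error, and the power gain is about 0 to 4 percentage points at SD 30. All of this depends on the assumed split, the assumed effect and an SD back-calculated from the plan's 17 per arm. The direct tie between hamstring harvest and flexor measures makes the same argument relevant to flexion strength and hamstring volume, although it cannot be sized there.

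**What to change.** 1. Record graft type, both planned and used, as study data.
2. Prespecify planned graft type, with graft-by-time, as fixed effects in the mixed model for strength and muscle volume. The interaction matters because harvest can affect only the visits after surgery; a graft effect held constant across all visits, including the pre-operative one, would not represent it.
3. If enrolment has not started and the graft choice is settled before randomisation, also run the block schedule separately for planned patellar tendon and planned hamstring grafts. Otherwise, make only the first two changes.

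**Cost.** One degree of freedom for the graft term. With time as a category, there are four interaction terms for the five strength visits and two for the three MRI scans. Stratifying needs a second block list and can leave overall group sizes slightly less equal when blocks are incomplete. If one graft is rare, stratifying gains little: at 90:10, that stratum would hold about 0.10 × 48 ≈ 5 patients. Naming the term before unblinding also avoids any challenge that it was chosen after seeing the data.

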5. Have a growth disorder of bones or connective tissue, type 1 diabetes mellitus, type 2 diabetes mellitus, or who have a history of carpal tunnel syndrome, trigger finger, myopathy, cancer, endocrine disorder, hypertension or rheumatologic disorder.
6. Systolic blood pressure >140mm Hg or diastolic blood pressure >90mm Hg, or with resting heart rate >110 BPM or <40 BPM at screening.
7. Additionally, because GH is currently listed as a banned substance by the World Anti-Doping Agency (WADA), National Collegiate Athletics Association (NCAA) and most professional sports agencies, we will exclude patients who are current collegiate, professional or elite athletes.

We will recruit up to 48 total patients (24 placebo control, 24 GH), recruited at a rate up to 3 to 6 patients per month. Interim data analysis will be performed, and actual sample sizes may be lower based on safety assessments and the effect of GH on strength.

We will exclude women from this study due to the consequences GH can have on reproductive cycles, and because GH can decrease the efficacy of birth control medications. Additionally, GH could have detrimental effects on a developing fetus. For these reasons, we are excluding women from participation in this study.

Screening Visit and Initial Study Measurements. Patients who consent to surgery and are interested in participating in the study will be seen at a screening visit. The screening visit will typically occur after a normal clinic visit, but may be scheduled at the convenience of the patient. The vital signs of patients will be measured, the history will be recorded, and patients will be asked to report to an M-Labs testing location for fasting blood work within the next 5 days. The labwork includes complete blood count with platelet differential, metabolic panel (glucose, urea nitrogen, creatinine, sodium, potassium, chloride, CO₂, calcium, total protein, albumin, total bilirubin, AST, ALT and alkaline phosphatase), lipid panel (total cholesterol, triglycerides, HDL cholesterol, LDL cholesterol), hemoglobin A_{1c}, high sensitivity CRP, creatine kinase, and IGF-1 (as described below). Patients who have normal values based upon M-Labs guidelines will be permitted to enroll in the study. Patients with minor deviations (typically less than 10%) from normal values may be allowed to participate based on consultation with [name] and [name]. Patients who do not pass screening will be provided with \$25 compensation.

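### Interim tests of strength may cut the sample size, but the plan fixes no tested week, boundary, final level or rule for counting patients already enrolled

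*Combined protocol and SAP*

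**What the plan says.** Two places describe the interim analysis. Patient Selection and Recruitment, in the paragraph after the exclusion criteria, says: "Interim data analysis will be performed, and actual sample sizes may be lower based on safety assessments and the effect of GH on strength". Sample Size and Statistical Analyses says: "We will also perform interim data analysis to determine if there are significant differences in strength and other outcomes between groups".

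Outcome Measures fixes the final endpoint: "The primary outcome measure of the study is isokinetic knee extension strength at 26 weeks". It treats strength at other visits separately: "Secondary outcome measures include isokinetic strength at other time points". Table 1 schedules isokinetic testing after surgery at about weeks 5, 12, 18 and 26; the week-5 row reads "Surveys, BioDex (isometric, isokinetic), MRI, blood draw, medication check, vital signs".

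The sample size is set "To detect a 30% difference in isokinetic knee strength between the placebo and GH group", with 80% power and a 0.05 level. That gives 17 per group, raised by 7 for attrition to 24 per group and 48 in total.

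On oversight, the Data and Safety Monitoring Plan has a committee review outcomes, strength included, every 3 months or as needed. Its grounds for halting are adverse events and harm, for example: "The committee may also stop the trial if there are any concerns that GH is causing harm". Randomization and Assignment of Groups lets group identities go to a named person and to "relevant members of the UMHS Pharmacy IDS and safety board members if necessary". The study team is unblinded after the last patient's discharge.

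**The concern.** Read together, the two interim sentences plan a between-group efficacy test that can shorten the trial. Strength is named separately from safety, so this is not a safety-only look. The 0.05 level belongs to a calculation with one test at the end. The plan does not say which week's strength is tested, how many looks there are or when, what result justifies a cut, whether the cut is for benefit or futility, what level the final test uses, or whether patients already enrolled are followed and counted.

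Two things are at stake. If a significant interim result were taken as the trial's result, its p-value would not carry the stated 5% error and the reported effect would be too large. If the cut rested on an early, non-primary visit, the 26-week test could be left with fewer patients than the plan says it requires. Outcome Measures uses these data to decide whether larger trials are warranted, so an inflated or weakened estimate has a direct consequence.

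**Working it through.** **Inputs from the documents.** Level 0.05, power 80%, 17 per group, plus 7, giving 24 per group and 48 in total (Sample Size and Statistical Analyses). Accrual of up to 3 to 6 per month (Patient Selection and Recruitment). First visit about 4 weeks before surgery (Table 1), or all screening within one week of surgery (Screening Visit and Initial Study Measurements); I use both, as 4 and 1 weeks.

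**Assumptions.** Two-sided tests (sidedness is not stated), steady accrual, a look at half of the outcomes, and a correlation of 0.6 to 0.8 between week-5 and week-26 strength.

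**1. The plan's own figure.** No SD is given, so 17 cannot be reproduced forwards. Solving the two-sample t-test for 80% power at 17 per group gives a standardized difference d = 0.991. If 30% means percentage points, SD = 30/0.991 = 30.3. The additions are right: 17 + 7 = 24, 2 × 24 = 48, and the allowance is 7/24 = 29.2%. With no dropout, power at 24 per group is 92%.

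**2. Upper bound: 0.05 at each look on 26-week strength, with a significant interim taken as the result.** The two test statistics have correlation √t, where t is the fraction of outcomes at the look. Type I error = 1 − P(|Z1| < 1.96 and |Z2| < 1.96).
- t = 0.5: 8.31%. t = 0.25: 9.07%. t = 0.75: 7.34%.
- Three equally spaced tests: 10.7%.
- Simulated t-tests at 12 then 24 per arm: 8.4%.

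At d = 0.991 and 12 per arm the noncentrality is 0.991 × √(12/2) = 2.43, and 64.1% of trials stop. Those trials report 1.22 SD on average; over all trials the mean is about 1.06 SD. With 9 or 8 per arm at the look, 50.6% or 45.5% stop.

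**3. Lower case: enrolment closes, and everyone enrolled is followed and tested once at 0.05.** Number enrolled when 24 patients have 26-week results = 24 + rate × lag, capped at 48. The lag is 27 weeks (6.21 months) or 30 weeks (6.90 months).
- 6 per month: 24 + 6 × 6.21 = 61, so all 48 are already enrolled. Error 5.0%.
- 3 per month: 24 + 3 × 6.21 = 42.6, or 24 + 3 × 6.90 = 44.7. Error 5.1% to 5.2%; mean estimate about 1.00 SD against a true 0.99.

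The plan says up to 3 to 6 per month, so slower accrual is possible. At assumed rates of 2 and 1 per month the error is 5.5% to 5.6% and 6.1% to 6.2%.

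**4. Look on week-5 strength, then followed as in step 3.** The lag is 6 weeks (1.38 months) or 9 weeks (2.07 months).
- 3 per month: 24 + 3 × 1.38 = 28.1, or 24 + 3 × 2.07 = 30.2.
- 6 per month: 24 + 6 × 1.38 = 32.3, or 24 + 6 × 2.07 = 36.4.

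So 14 to 18 per arm are enrolled at closure. If the full allowance is lost (× 17/24), 10 to 13 per arm remain. Type I error is 5.2% to 5.7%. Power of the 26-week test at d = 0.991, over trials that close early and trials that do not:

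| Attrition | Effect at week 5 | Power | Without a cut |
|---|---|---|---|
| Full 7 of 24 | 0.99 SD | 72% to 77% | 80% |
| Full 7 of 24 | 0.5 SD (assumed) | 79% to 80% | 80% |
| None | 0.99 SD | 84% to 89% | 92% |

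**5. A specified rule.** Two-sided p<0.001 at the half-way look and 0.05 at the end gives 5.02% by the formula in step 2. Power at 17 per group stays at about 80%. At d = 0.991 the look crosses the boundary in 12.5% of trials at 12 per arm, and in 6.4% and 4.8% at 9 and 8 per arm. A futility-only cut (stop if |z| < 0.5 half-way, assumed) gives 4.7%, so it does not inflate the error.

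**The case against.** The strongest reply is that the larger figures describe a trial nobody has proposed. The 8.3% needs an unadjusted 0.05 at the look and an interim result treated as final. The plan says only that sample sizes may be lower, which is most naturally read as closing enrolment. Table 1 follows each patient to about week 26, and the team stays blinded until the last discharge. On that reading, at the planned accrual, the error is 5.2% or less and bias is small. This stands, and it is why 8.3% is given only as an upper bound. It does not remove the gap, because no section states how enrolled patients are counted or at what level they are tested.

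The power loss is also conditional. The 72% to 77% needs both the whole attrition allowance and the full effect by week 5; with no dropout, power stays above the planned 80%. A reader might infer that an early cut would leave the trial underpowered. The documents support only that it could.

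A reader might also infer that nobody is placed to see interim strength data, or that the look must break the blind. Neither follows. The committee reviews strength every 3 months, and safety board members may be given group identities if necessary. Because the groups carry colour codes, a coded comparison is possible without formal unblinding. What is missing is narrower: the review is not linked to the interim analysis, carries no efficacy criterion, and sits beside stopping grounds that concern harm. Nor do the documents support counting each 3-monthly review as an efficacy look.

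Finally, this is a pilot that puts safety first. That lowers the stakes, but the plan still sets a primary outcome, a level and a power.

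**Conclusion.** The point holds as an unspecified decision rule, and it should be fixed. The plan commits to interim significance tests of strength and lets the sample size respond to them, yet its only error rate belongs to a single-look calculation. I am confident of the omission; its size depends on conduct that the plan leaves open. At the planned accrual, type I error runs from about 5.0% to 5.2% (everyone followed, one final test) up to 8.3% (one unadjusted half-way look taken as the result). In the upper case, trials that stop at 12 per arm report about 1.22 SD against a true 0.99 SD. A week-5 cut can take the 26-week test below 17 per group, with power from 72% to 89% depending on dropout and on the effect at week 5.

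These figures rest on two-sided testing, a look at half of the outcomes, d = 0.99 worked back from the plan's N, and the assumed correlations. The documents do not support saying that the trial will test at 0.05 at each look, or that its error rate is 8.3%.

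**What to change.** In Patient Selection and Recruitment and in Sample Size and Statistical Analyses, state that:

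- There is one interim comparison, of 26-week isokinetic knee extension strength, when 24 of the planned 48 patients have 26-week outcomes (or half of those expected after attrition, 17 of 34). Only the safety committee sees it.
- Enrolment may close for benefit only at two-sided p<0.001 (Haybittle-Peto), and the final test is at 0.05. Another alpha-spending boundary would also do.
- All enrolled patients are followed to 26 weeks and are in the final analysis.
- Interim results for other weeks and other outcomes are descriptive and cannot change the sample size.
- Any futility stop is non-binding and spends no alpha.

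In the Data and Safety Monitoring Plan, state that the 3-monthly strength review is for safety, and that group-level strength results, coded or not, stay with the committee until the last discharge. In Randomization and Assignment of Groups, name the role that prepares the interim table.

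A simpler alternative is to allow reductions for safety only, with no between-group efficacy test before the last 26-week visit.

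**Cost.** These are short wording edits; N is unchanged, and the overall error is 5.02% with power of about 80% at 17 per group. The price is flexibility. At 0.99 SD and 12 per arm, early closure for benefit falls from 64% to about 12%. A 26-week look spares only 0 to 5 of 48 enrolments at 6 to 3 per month, so the average saving is under one patient (0.125 × 5 is about 0.6). A week-5 look could have spared 12 to 20. That small saving favours the simpler alternative, which in turn gives up futility stopping: an assumed |t| < 0.5 rule at 8 to 12 per arm would stop about 38% of trials with no effect.
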